We propose a randomized controlled design for this pilot 12-week trial of the behavioral intervention MET compared to KK+KY for improving cognitive performance and health in women at high risk of AD. We hope to control for nonspecific factors by using a gold standard active control condition that has demonstrated acceptability in this population.

The proposed study will to test whether KK+KY is superior to MET for improving cognitive functioning, health (including cardiovascular factors), and mood in women with high AD risk. All participants will be recruited from the UCLA Women's Cardiovascular Center, UCLA outpatient clinics and the UCLA Longevity Center Program. All participants will be identified as having high AD risk including subjective memory complaints and high cardiovascular risk based on the 2013 ACC/AHA Guideline on the Assessment of Cardiovascular Risk (Goff et al., 2014). Follow up of all enrolled subjects at 6- and 12-months (52 weeks total) will allow detection of any continued cognitive or health benefits.

b) Methods for reducing risk of bias:

Participants will be informed prior to enrollment that they will receive one of two evidence-based interventions for improving memory. Descriptions of the study will be designed to minimize risk of possible between group differences resulting from differences in treatment expectancy. Differences in treatment expectancy/ credibility will be tested for at baseline, week 12, and week 24 as specified below. We will also control for the "instructor" effect if several instructors teach classes. The feasibility of weekly yoga/MET classes and homework time was assessed during previous studies and found reasonable for participants to complete (Eyre et al., 2016; H. Yang et al., 2016). Behavioral raters will be blind to group assignment.

1. Study Population: We anticipate screening about 250 subjects to recruit 100 women with subjective memory complaints and high cardiovascular risk based on the 2013 ACC/AHA Guideline on the Assessment of Cardiovascular Risk. Participants will be recruited from the women's clinics and geriatric clinics at UCLA as well as the UCLA Longevity Center.

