Autonomic nervous system (ANS) and respiratory measures. In order to link genotype and neuroimaging data with respiratory and ANS functioning, we will perform a series of five tests: 1) rest; 2) paced breathing; 3) breath hold; 4) Valsalva maneuver; 5) hand grip. These tasks will provide detailed information about cardiorespiratory functioning. Continuous blood pressure will be assessed using a probe attached to two fingers of the same hand. An additional finger probe will be used to measure the Galvanic skin response (GSR) and chest electrodes will be applied for the electrocardiogram (ECG) and on the hand for an electromyogram (EMG). A respiratory belt around the patient's chest will provide breath rate data and a small probe attached to the cheek will measure changes in face skin temperature. End-tidal CO2 will be measured using a capnometer and spirometry will be used to investigate pulmonary capacity. Verbal instructions will be provided and a computerized task will indicate to the subjects when to begin and end each challenge, for example when to prepare for the breath hold (deep inhale followed by deep exhale and then hold at the top of the next deep inhale). Data will be recorded and time-locked using a BioPac system and associated software, which will also be used to process the data.

Randomization and treatment schedule:

After all screening and baseline test results are reviewed and eligibility criteria are confirmed, patients will sign the informed consent form. Next, participants will be randomized to either MET or KK+KY groups using a computer-generated random assignment scheme, which assigns participants in a 1:1 ratio to each group using a customized module built into the centralized data system. All behavioral raters will be blind to the group assignment, and participants will be asked not to disclose their group assignment to the raters.

Study intervention procedures:

Participants will be randomized to: (1) MET class for 60 minutes per week plus daily homework; or (2) KY class for 60 minutes per week plus daily KK homework. Participants will complete a questionnaire about their treatment expectations after their second class. Follow-up assessments immediately after the intervention (12 weeks) as well as at 24 and 48 weeks will test the effect of the interventions at both short- and long-term follow-up.

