Memory Enhancement Training Intervention. Patients will be informed that MET teaches specific memory strategies and has been shown to improve memory in adults with mild cognitive impairment. The standard detailed protocol for MET program is based on evidence based techniques that use verbal and visual association strategies and practical strategies for memory compensation (Gross et al., 2012; Verhaeghen et al., 1992). The MET program is manualized and includes components adapted from other effective memory training programs (Verhaeghen et al., 1992) such as: (1) Education about memory; (2) Preliminary instruction in the basic elements of memory strategies (i.e. "pre-training"); (3) Instruction in specific memory strategies; (4) Home practice with logs to track activity; (5) Addressing non-cognitive factors such as self-confidence, anxiety, and negative expectations; (6) Small (i.e. 10 persons) groups and short (60 min) sessions. The curriculum is divided into 12 weekly sessions which are organized in the same way in which trainers: (1) Document attendance, collect homework completion logs and assess engagement in alternative treatments; (2) Review the previous session's homework in order to reinforce home practice; (3) teach new techniques, reviews, and conduct in-class exercises, (4) assign homework for the upcoming week. Overall, in each session, roughly 15 minutes are devoted to reviewing the homework and 45 minutes is devoted to learning and practicing techniques. Specific techniques include: Visual associative learning strategies for learning faces and names (adapted from McCarty, 1980)(McCarty, 1980), verbal associative techniques such as the use of stories to remember lists: organizational strategies (categorizing items on a grocery list); forming good memory habits to recall where one places items, what one has done in the recent past (e.g. locking doors, turning off appliances); and how to remember future tasks (i.e., appointments). [name], a postdoctoral fellow supervised by [name], or a masters-level trainee supervised by [name] will teach the MET intervention.

KK+KY intervention:

Kundalini yoga (KY) class will be scheduled for 60 minutes weekly and will be conducted by a certified yoga teacher. The content and structure of the class will be similar across weeks: 1) Tuning in (5 minutes); 2) Warm up (10 minutes); 3) Pranayam (10 minutes); 3) Kriya (20 minutes); 4) Meditation (12 minutes) 5) Shavasana (3 minutes).

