Kirtan Kriya (KK). Participants will be asked to engage in 12 minutes of daily KK meditation. Meditations will be guided by standardized CDs distributed to participants that can be practiced at home. The protocol for KK is a standard ancient chanting meditation for the Kundalini Yoga practice as taught by Yogi Bhajan and as utilized in previous studies in older adults (Andrew B. Newberg, Wintering, Khalsa, Roggenkamp, & Waldmanb, 2012). The meditation involves repetitive finger movements or mudras, as well as chanting of the mantra "Saa, Taa, Naa, Maa," meaning "Birth, Life, Death, and Rebirth" first chanted aloud, then in a whisper, and silently for the total of 11 minutes with 1 minute allocated to "tuning in" at the beginning and the final deep breathing relaxation accompanied by the visualization of light.

Alternate treatments. All participants will be medically stable prior to entry into the study protocol. However, if participants engage in alternate treatments, they will be advised to inform the PI. Upon completion of the research procedures, yoga classes will be offered to participants who participated in MET and vice versa.

Treatment expectancy/ credibility. Our study has been designed to promote equal perception of treatment expectancy/ credibility between groups. We will evaluate treatment credibility, expectation for change, and satisfaction after the 2nd session of treatment and at post-intervention using a 10-point Likert scale, as we have done in our pilot study.

Dosing effects. We will distribute and collect home practice logs to determine the relationship between practice and outcomes. The extent to which participants continue to practice skills learned during the intervention period will also be assessed at 6-month and 12-month follow up. As in previous studies, we will also ask participants in both intervention groups to keep a brief weekly journal about any changes they have noticed that they attribute to the intervention. This data will be analyze through qualitative analysis at the completion of the study. **Data analysis.** Primary analyses will be carried out on an intent-to-treat basis; additional analyses considering dropout or other observable post-randomization outcomes will make use of an instrumental-variable analysis framework.

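### The written arm descriptions credit only MET with a demonstrated memory benefit, and the expectancy checks promised at baseline and week 24 do not match what is scheduled

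*Combined protocol and SAP*

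**What the plan says.** **Reliance on equal expectancy.** Study Design, b) Methods for reducing risk of bias, says that study descriptions will be designed to limit between-arm differences in expectancy. It gives a common statement: "Participants will be informed prior to enrollment that they will receive one of two evidence-based interventions for improving memory". It then commits to a check: "Differences in treatment expectancy/ credibility will be tested for at baseline, week 12, and week 24 as specified below". The later paragraph on treatment expectancy/credibility repeats the aim of equal perception between groups. Behavioral raters are blind; participants know their class.

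**What is scheduled.** Study intervention procedures: "Participants will complete a questionnaire about their treatment expectations after their second class". The treatment expectancy/credibility paragraph collects credibility, "expectation for change, and satisfaction after the 2nd session of treatment and at post-intervention using a 10-point Likert scale". In Table 4 the treatment credibility row has an entry marked week 2 in the Baseline column and one further entry, at week 12 by column order. There is nothing at week 24 or week 48.

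**What is said about each arm.** The section describing MET reads: "Patients will be informed that MET teaches specific memory strategies and has been shown to improve memory in adults with mild cognitive impairment". That section also lists as a curriculum component "Addressing non-cognitive factors such as self-confidence, anxiety, and negative expectations". The KK+KY text describes the class structure, the home practice ("Participants will be asked to engage in 12 minutes of daily KK meditation") and the recordings. It contains no statement about efficacy.

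**Analysis.** The Data analysis and Power analysis sections name no analysis that uses the expectancy scores.

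**The concern.** Memory performance is the primary outcome. It is measured by tests that depend partly on effort, in women who know their arm. Several secondary outcomes (depression, stress, quality of life, memory complaints) are self-reported. If one intervention is presented as proven for memory and the other only as a practice to follow, women may come to expect different things from the two arms. Part of any memory difference could then reflect expectation.

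The plan names its own safeguard: compare expectancy between arms at three times. As scheduled, the first comparison comes after two classes, so it cannot describe the arms before exposure. The last promised comparison is missing, which leaves the 6-month follow-up without one. A bias control stated in the design section is therefore only partly delivered.

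**Working it through.** **1. Time points, side by side.**

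| Source | Before treatment | Week 2 | Week 12 | Week 24 |
|---|---|---|---|---|
| Methods for reducing risk of bias | yes (baseline) | – | yes | yes |
| Study intervention procedures | – | yes | – | – |
| Treatment expectancy/credibility | – | yes | yes | – |
| Table 4 | – | yes, under Baseline | yes | – |

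Three are promised, two are scheduled, and only week 12 agrees. The class-2 form necessarily follows randomisation, because classes start after allocation.

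**2. Arm descriptions, side by side.** MET has an efficacy sentence about memory. KK+KY has none. A parallel sentence was available: the summary of the earlier MCI trial (Preliminary data, item 2) reports significant memory improvement in both groups at 12 and 24 weeks.

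**3. The plan's own power figure.** Inputs from Power analysis: 45 per group, equivalence margin 0.62 (read as SD units), true difference 0. Assumed: SD = 1 and 0.05 per one-sided test. Standard error = √(2/45) = 0.211. Power = 2Φ(0.62/0.211 − 1.645) − 1 = 0.805, against 80% stated (0.797 with the t distribution). The figure reproduces, and nothing here disputes it.

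**4. What a significance test of expectancy can show.** Two-sided 0.05 t-test, 45 per arm:

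| True expectancy gap (SD) | Power |
|---|---|
| 0.2 | 0.155 |
| 0.3 | 0.291 |
| 0.4 | 0.467 |
| 0.5 | 0.650 |

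Power reaches 80% only at a gap of about 0.60 SD. The 95% confidence interval has half-width 1.99 × 0.211 = 0.42 SD. If all 50 per arm complete the week-2 form, it is 1.98 × √(2/50) = 0.40 SD. A non-significant result would therefore leave a moderate gap open, and an interval would show this.

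**5. Consequence for the primary comparison (illustration only).** The documents give no effect of expectancy on memory. Suppose expectancy moves the true memory difference by b SD. Equivalence power is then Φ((0.62 − b)/0.211 − 1.645) + Φ((0.62 + b)/0.211 − 1.645) − 1:

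| Assumed b (SD) | Equivalence power |
|---|---|
| 0 | 0.805 |
| 0.1 | 0.756 |
| 0.2 | 0.623 |
| 0.3 | 0.446 |

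**The case against.** The strongest reply is that the plan already deals with expectancy. Every woman is told before enrolment that both interventions are evidence-based for improving memory, which is an efficacy statement covering KK+KY. Raters are blind, and the primary outcome is a composite of performance tests. Credibility and expectation are measured in both arms, including at week 12, the primary time point. Table 4 openly marks its Baseline entry as week 2. Work on negative expectations is a manualised part of MET, so its effect belongs to the intervention being compared.

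Much of this stands, and it rules out some stronger readings that a reader might draw:

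- **That an expectancy gap is created, or that KK+KY women hear nothing about efficacy.** The MET sentence does not say when it is given, or that only women allocated to MET hear it. The participant scripts are not in the document. The text shows an asymmetry in the written descriptions, hence a risk.
- **That expectancy cannot be separated from treatment at all.** Scores at week 2 and week 12 in both arms allow a gap to be measured. What is missing is a pre-exposure value, the week-24 value and a stated analysis.
- **That adjusting for a pre-randomisation score would cure the problem.** Randomisation already balances prior expectancy on average. Expectancy produced after allocation is neither detected nor removed by such a covariate.
- **That the bias has a known size.** Assuming an expectancy shift of 0.3 to 0.5 SD and a slope of 0.2 to 0.3 on memory gives 0.3 × 0.2 = 0.06 to 0.5 × 0.3 = 0.15 SD. Neither input comes from the documents.

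The reply does not remove the contradiction over time points, nor the one-sided efficacy sentence. Blind raters guard against biased scoring, but not against differences in participants' effort.

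**Conclusion.** The point holds as an inconsistency in the schedule together with a risk in the wording. The promised week-24 check is unscheduled. The check called baseline is taken after randomisation and two classes. The efficacy sentence about the primary outcome appears for MET alone, although the common pre-enrolment statement softens this. No power or sample-size figure is wrong on this account.

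The firm size is one matching time point out of three promised. The low power of an expectancy test (about 29% for a 0.3 SD gap) assumes 45 per arm and a simple two-group comparison. The loss of equivalence power depends on assumed shifts and shows only why the check deserves to work as stated. The changes are worth making because they are nearly free and deliver a control that the plan already claims.

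**What to change.** 1. **Wording.** Use parallel efficacy statements for both interventions, which the earlier MCI trial's results in both groups would allow, or delete the MET sentence.
2. **Schedule.** Reconcile Methods for reducing risk of bias with Study intervention procedures, the treatment expectancy/credibility paragraph and Table 4. Relabel the class-2 form as week 2, add the promised week-24 form, and add a short form before randomisation on which each woman not yet randomised rates both interventions.
3. **Analysis.** State that the between-arm difference in expectancy/credibility will be reported with a 95% confidence interval at week 2 and week 12, as the check for an expectancy gap. Do not treat a non-significant test as evidence of equal expectancy. Use any pre-randomisation score only as an optional precision covariate, not as a correction for expectancy arising after allocation.

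Cost: edited text and a few minutes of form completion at existing visits. Women already randomised will lack the pre-randomisation score; the wording and analysis changes do not depend on it, nor does the week-24 form for women who have yet to reach that visit.

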Specifically, we aim to investigate the neurobiological mechanistic response of women to memory enhancement training (MET) compared to combined Kundalini yoga (KY) and Kirtan Kriya (KK, a Kundalini yoga meditation) through a randomized study targeting women with high AD risk. For the purposes of this study, women with high risk for AD are defined as women with high cardiovascular risk (Ho, Pinsky, Kannel, & Levy, 1993; Truelsen, Lindenstrom, & Boysen, 1994) and subjective memory complaints. The methodology for this study is based on our study of individuals with MCI randomized to either combined KK+KY or to memory enhancement training (MET) (B. P. Acevedo et al., 2016; Eyre et al., 2016; Eyre et al., 2017; H. Yang et al., 2016). Compared to MET, KK+KY demonstrated short- and long-term benefits in executive functioning, as well as broader effects on depressed mood and resilience. The positive outcomes of this study suggest that KK+KY may be a promising intervention for reducing risk for AD in women. Our study sample will consist of 100 women over the age of 50 with high risk of developing AD. Participants will be randomized to 12 weeks of either KK+KY or MET. The primary outcome is memory performance. Secondary outcomes include executive functioning, brain structure and connectivity. The benefit of interventions will be determined at 12 weeks and at 6- and 12- month follow-up. The proposed study will test the mechanisms and efficacy of the proposed interventions to improve memory and cognitive performance, mood, resilience and quality of life in older women, with the purpose of reducing AD risk in this population. We will use the proposed model to develop preventive interventions for women at high-risk for developing AD.

Introduction:

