We designed the present randomized trial to test whether 12 weeks of supervised weekly Kundalini yoga class and a brief daily home meditation practice can improve cognitive function among older women with high AD risk compared to weekly classes of memory training with daily homework. Our choice of interventions is based on prior studies of mind-body exercise in older adults that revealed robust cognitive benefit, as well as our own studies of this intervention compared to cognitive memory training in older adults with MCI. Kundalini yoga has also been observed to impact the frontal lobes, likely due to increased cerebral blood flow ([name] et al., 2013b).

The primary outcome will be memory performance at 12 weeks (i.e., immediately post-treatment).

Secondary outcomes include measures of executive functioning and changes in brain structure and connectivity.

Specific Aim 1: To evaluate effects of Kundalini Yoga+ Kirtan Kriya (KK+KY) and Memory Enhancement Training (MET) on memory performance in women with high AD risk.

Hypothesis 1: Improved memory performance will be observed in women receiving KK+KY and MET at 12 weeks compared to baseline.

Specific Aim 2: To test the efficacy of KK+KY vs. MET for improving executive functioning including working memory.

Hypothesis 2: KK+KY will improve performance in executive functioning to a greater extent than MET.

Exploratory Aim 3a: To test the effects of MET vs. KK+KY on structural and functional connectivity and task-related activation for working and episodic memory.

Hypothesis 3a: Compared to MET, KK+KY will be associated with greater improvement in connectivity in regions associated with working and episodic memory.

Exploratory Aim 3b: To test the effects of MET vs. KK+KY on levels of cellular and genomic markers of inflammation, telomerase activity level, and telomere length after 12 weeks and at 6 and 12 month follow-up.

Hypothesis 3b: Compared to MET, KK+KY will be associated with decreases in cellular and genomic markers of inflammation and increases in telomerase activity level and telomere length after 12 weeks and at 6 and 12 month follow-up.

Exploratory Aim 3c: To explore whether KK+KY results in reduced cardiovascular risk factors compared to MET, and whether this effect will correlate temporally with changes in fMRI measures and clinical outcomes.

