Measures and Outcomes: All instruments provide a comprehensive assessment of cognition, mood, quality of life, well-being, mindfulness and resilience. Diagnosis will be determined on study entry. *All outcome measures will be administered at baseline, week 12, and 6 and 12 months, or upon early termination. Primary and secondary outcome and safety measures will be administered at each assessment visit.*

The Hopkins Verbal Learning Test-Revised (HVLT-R)(Benedict, Schretlen, Groninger, & Brandt, 1998) delayed recall will be administered at baseline to identify memory impairment.

The Beck Depression Inventory will be used to rule out current clinically-significant depressive symptoms.

Inter-rater reliability for all instruments will be established at the beginning of the trial. Drs. [name] and [name] will administer clinician-administered instruments and will be trained to reliability (current inter-rater correlation coefficient (ICC) \geq 0.9.).

Assessment: Memory performance as determined by neuropsychological evaluation (described below) is the primary outcome of interest. Behavioral outcome assessments will be performed by raters blind to treatment assignment.

Domain	Test	Administration Time
	HVLT (delayed recall)	30 min
Memory	WMS-IV (Logical Memory II delayed recall)	30 min
	Rey-Osterreith Complex Figure 3-min Delay	5 min
Executive Function/	Stroop Interference	5 min (computerized)
working memory	Trails B	5 min
	Trails A	3 min
Attention/ processing speed	Digit Span	5 min
	Stroop color and word	(no time added)
	CFL/FAS/PRW fluency	3 min
Language Fluency	Animal Fluency	1 min
	Boston Naming Test	15 min
Premorbid Cognitive Function	Wechsler TOPF	5 min

 Table 3. Neuropsychological test battery

Neuropsychological tests will be administered at baseline and at the 6- and 12-month follow-up. We will use a focused test battery developed by [name] that is highly sensitive to memory deficits. Because memory function is the main target of MET interventions, this will be the primary outcome. Specifically, **the primary**

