Pain will be assessed via the Brief Pain Inventory (BPI) Short Form, a validated scale for rapidly assessing the severity of pain and its impact on functioning (Cleeland, 1989).

Safety Evaluations: All participants will be interviewed about their recent history of psychiatric and medical illnesses, psychosocial stressors, and current medications. We will use the UKU Side Effect Rating Scale (Lingjærde, Ahlfors, Bech, Dencker, & Elgen, 1987), a rating scale for monitoring adverse events which will be completed at each assessment visit.

Domains of Assessment	Screen	Baseline	Week 6 (after class)	Week 12	Week 24	Week 48
Cognitive						
Clinical Dementia Rating	Х					
MMSE	Х			Х	Х	Х
Neuropsychological battery		Х			Х	Х
Memory Functioning	Х			Х	Х	Х
Psychosocial						
Beck Depression Inventory	Х			Х	Х	Х
Hamilton Anxiety	Х			Х	Х	Х
Perceived Stress Scale	Х			Х	Х	Х

Table 4. Assessment schedule.

Resilience (CD-RISC Scale)	х			x	x	x
Emotion Regulation	Х		Х	Х	Х	Х
SF-36 (QOL)	Х			Х	Х	Х
Duke Social Support	Х			Х	Х	Х
Monetary Choice	Х			Х	Х	Х
Medical						
CIRS-G	Х			Х		
Stroke Risk	Х			Х		
Clinical ECG	Х					
Brief Pain Inventory	Х			Х	Х	
Other						
Demographics / medical and reproductive history and medications	х					
Monitoring for new treatments		х	Х	X	Х	x
Treatment credibility		X (wk 2)		Х		
Clinical Global Improvement				X	х	x
Family history of dementia	Х					
Physical Activity and Meditation Practice	Х			Х	х	X
Adverse reactions		Х	Х	Х	Х	Х
Cellular Biomarkers						
Telomerase levels		Х		Х	Х	
Telomere length		Х		Х	Х	
Cardiac Biomarkers						
Lipid panel, hsCRP, HbA1c, TSH, electrolytes, CBC		x		х	х	
BP, HR, weight		Х		Х	Х	Х
Molecular Biomarkers						
Cytokine gene polymorphisms		x		x	х	
Microarrays (GWAS expression)		X		Х	х	
Imaging Biomarkers						
Structural MRI		Х		Х		
fMRI		Х		Х		
ANS Biomarkers						

Breathing rate	X	X	X	
End-tidal CO ₂	X	Х	Х	
ECG	X	Х	Х	
Continuous blood pressure	X	Х	Х	
Skin face temperature	X	X	Х	
Electromyogram	Х	Х	Х	
Spirometry	X	X	Х	
Galvanic skin response	X	Х	Х	
ANS challenges	X	X	Х	

Inflammatory biomarkers: Inflammatory signaling will be measured by assay of activation of NF-κB using intranuclear staining and flow cytometric analyses, given its associations with mood (Koo, Russo, Ferguson, Nestler, & Duman, 2010; Pace & Miller, 2009).

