In the fitting method, f(i) is CBF at each individual delay and the final CBF is the mean of the estimated CBF per PLD. The 5 PLDs allow us to estimate CBF and ATT simultaneously using parameters fitting (2). Resulting rCBF and ATT maps will then be co-registered with the T1-weighted structural scan and normalized to the MNI standard space template with subsequent spatial smoothing.

WM Hyperintensities (WMH). The 3D T2-space images will be used to visualize WMHs by employing a semiautomated WMH identifier (Schwarz, Fletcher, DeCarli, & Carmichael). Briefly, WMH burden will be assessed based on the signal intensities of co-registered 3D MEMPR and T2-SPACE images, and population statistics on the spatial distribution and neighborhood structure of WM lesions. With every unit increase in WM burden, we will estimate % reduction in local brain tissue volume. GLM and multiple regression analyses will determine links between WM burden, clinical measures and vascular risk factors in each treatment group that may need to be controlled for.

Integration with Mood and Neurocognitive Measures. To test hypotheses about the relationships between imaging metrics and change in mood and cognition, we will derive domain summary scores for the 3 domains of interest – i.e., mood, memory, and executive functioning. Percent change in the mean Z scores will be calculated for each domain score and entered into analysis. We will first test the specific hypotheses described in the aims using separate GLMs for each MRI method. *Integration of Predictive Variables.* After analysis is complete on the predictive validity of each MRI measure, those that significantly predict remission/relapse or cognitive decline at follow-up will be combined for regression analysis. We will use the best single predictor in each modality. The final analysis will include a step-wise multiple regression analysis of clinical outcomes.

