Primary outcome: The analyses for the memory domain Z scores will use general linear mixed model (GLMM) analysis (e.g., SAS PROC MIXED). The two treatment groups will be compared for time course of cognitive domain z scores the initial endpoint EOT at 12 weeks and 6- and 12-months. Covariates may be included in the model as noted above. As noted above, the primary cognitive domain of interest for this proposal is memory. A separate GLMM as above will be estimated using memory domain z-scores as dependent variables. Executive Function will be examined as secondary outcome measure. Supplementary analyses of the follow-up period will look at the cognitive domain scores by treatment group controlling for values at EOT (post-treatment changes). Objective memory measures will be examined using a similar GLMM.

Exploratory Hypotheses: GLMM models as described above will be used to examine telomerase activity (overall level and TL) and inflammatory measures separately. Relationships between changes in markers of inflammation and telomerase activity to changes in cognitive scores, cognitive domain scores and fMRI measures will be examined using regression models within each group. Transformations of the measures will be performed as necessary.

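### The neuropsychological battery that forms the primary outcome is not scheduled at week 12, the time point of the primary endpoint

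*Combined protocol and SAP*

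**What the plan says.** The Proposed Intervention section states that the primary outcome "will be memory performance at 12 weeks (i.e., immediately post-treatment", and Hypothesis 1 compares week 12 with baseline. The neuropsychological tests paragraph defines the outcome as the mean z-score over the HVLT, the WMS-IV and the Rey-Osterreith figure. All three belong to the Table 3 battery, as do Trails B and Stroop, the executive-function secondary outcome.

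On timing, the protocol says two different things.

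- **Week 12 included.** Measures and Outcomes: "All outcome measures will be administered at baseline, week 12, and 6 and 12 months, or upon early termination". The abstract: "The benefit of interventions will be determined at 12 weeks and at 6- and 12- month follow-up". Study intervention procedures: "Follow-up assessments immediately after the intervention (12 weeks) as well as at 24 and 48 weeks will test the effect of the interventions". The primary-outcome analysis also takes end of treatment at 12 weeks as its initial endpoint.
- **Week 12 left out.** The neuropsychological tests paragraph says the battery "will be administered at baseline and at the 6- and 12-month follow-up". In Table 4 the row "Neuropsychological battery" is marked at Baseline, Week 24 and Week 48, with Week 12 blank.

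**The concern.** The only two statements that schedule the battery by name both omit the visit at which the primary endpoint is defined. No precedence rule resolves the conflict, and a visit table is what staff normally work from. If it is followed:

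- There is no week-12 memory composite, hence no primary endpoint.
- There is no week-12 Trails B or Stroop score.
- The analysis described as "Supplementary analyses of the follow-up period will look at the cognitive domain scores by treatment group controlling for values at EOT" has no end-of-treatment value to condition on.
- The second MRI is at week 12, and the imaging section says: "To test hypotheses about the relationships between imaging metrics and change in mood and cognition, we will derive domain summary scores". No battery-based memory or executive score would be concurrent with that scan.

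Other data would still exist. At week 12 there would be the MRI, the MMSE, the Memory Functioning questionnaire and the in-scanner N-back and face-name responses. Battery scores would follow at weeks 24 and 48. None of these is the defined primary outcome. The linear mixed model allows scores missing at random, but it cannot estimate a week-12 group effect on the composite when nobody is tested at that visit.

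**Working it through.** **Is the blank cell real?** The Table 4 columns are Screen, Baseline, Week 6, Week 12, Week 24 and Week 48. The battery row reads: blank, X, blank, blank, X, X. The adjacent MMSE and Memory Functioning rows carry a Week 12 mark in the right place, so the table was extracted in order. The stronger evidence is that the prose independently gives the same three time points. A mark lost in the PDF does not explain both.

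**The plan's own power figure.** Inputs from Power analysis: 45 per group, margin 0.62, true difference 0, power 80%. Assumptions: the margin is in SD units, and each one-sided equivalence test is at 0.05 (the level is not stated for the equivalence test).

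Normal approximation: power = 2Φ(0.62/√(2/n) − 1.645) − 1. With n = 45, √(2/45) = 0.2108 and 0.62/0.2108 = 2.941, so power = 2Φ(1.296) − 1 = 80.5%. The exact t version gives 79.7%. The stated 80% is reproduced, and it rests on the 45 per group expected at 12 weeks. For executive function, a two-sided t-test at 0.05 with d = 0.60 and n = 45 gives 80.4%, which also agrees.

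**If the first repeat were at week 24.** Recruitment gives 45 per group at 12 weeks and 35–36 at 12 months, but no 6-month count. Applying 10% twice gives 50 × 0.9 × 0.9 = 40.5; subtracting 5 twice gives 50 − 5 − 5 = 40. So 40–41 is an inference, and 35–36 serves as a lower bound.

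| n per group | Basis | Equivalence, margin 0.62 (exact t) | Executive function, d = 0.60 |
|---|---|---|---|
| 45 | stated, week 12 | 79.7% | 80.4% |
| 41 | inferred, week 24 | 74.5% | 76.5% |
| 40 | inferred, week 24 | 73.0% | 75.5% |
| 36 | stated, 12 months | 66.3% | 70.9% |
| 35 | stated, 12 months | 64.4% | 69.7% |

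**Testing time at week 12 (Table 3).** Full battery: 30 + 30 + 5 + 5 + 5 + 3 + 5 + 0 + 3 + 1 + 15 + 5 = 107 minutes. The three memory tests take 30 + 30 + 5 = 65 minutes; adding Stroop (5) and Trails B (5) gives 75.

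**The case against.** The best reply is that the intent is plain. Besides the general statement, the next sentence in Measures and Outcomes puts primary and secondary measures at every assessment visit, and the aims, the intervention section and the analysis all presuppose testing at 12 weeks. On that view this is a scheduling slip, not a design without a week-12 test.

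That stands as a reading of intent, but it does not remove the conflict. The general statement cannot be taken literally for every outcome: brain structure and connectivity are secondary outcomes, yet MRI is scheduled only at baseline and week 12. A reader therefore has good reason to let the measure-specific schedule govern, and for the battery that schedule omits week 12.

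Four narrower objections have some force.

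- **Power.** The week-24 and 12-month figures describe a fallback that nobody proposes. They are two-sample calculations on completers, whereas the plan uses a mixed model. They illustrate the loss and do not carry the conclusion.
- **Imaging.** The imaging section does not say at which visit cognitive change is taken, so pairing it with the week-12 scan is a plausible reading and not a stated requirement.
- **Testing burden.** A fourth administration is new only relative to the battery schedule; the general statement already implies four.
- **Testing time.** The 107 minutes includes 5 for the TOPF, which estimates premorbid function and is not an outcome.

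**Conclusion.** The contradiction is confirmed. The protocol defines a 12-week primary endpoint, and both schedules specific to its instrument leave that visit out. Read literally, they yield 0 of the roughly 90 week-12 composites assumed in the power statement, and a missed week-12 test cannot be obtained afterwards. That alone makes the correction essential.

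The power losses apply only if the battery schedule is followed in place of the general statement. They also rest on three assumptions: a margin in SD units, one-sided 0.05 per equivalence test, and an inferred week-24 count. Once the schedule is corrected, the stated 80% with 45 per group stands.

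**What to change.** Mark the neuropsychological battery at Week 12 in Table 4, and change the sentence to list baseline, week 12, and the 6- and 12-month follow-ups. Both then agree with the primary endpoint and the general statement.

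The cost is one table mark and one sentence at an existing visit, with up to 107 minutes of testing there, or 75 minutes for the memory tests, Stroop and Trails B alone. Compared with the battery schedule as written, each woman is tested four times and not three. The protocol says that most measures, not all, have two or four alternate forms. Measures with two forms or none would therefore repeat material, and the added practice exposure falls on weeks 24 and 48. Stating the order of forms by visit would make this explicit.

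Separately, and of minor weight: Exploratory Aim 3b asks for biomarker effects at 12 months, while blood is drawn only at baseline, 12 weeks and 6 months. Those passages should be reconciled in the same amendment.
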